Official Title: Does Endurance Improve with the use of Passy-Muir Valve for Patients with Tracheostomy?

Clinical Trial Number: NCT04941456

Study Closeout: June 24, 2024

STUDY PROTOCOL AND STATISTICAL ANALYSIS PLAN

Methods

Research design: Six period Quasi-Randomized Crossover Controlled Study. Enrollment will occur based off tracheostomy census report, site investigators will perform weekly pull of tracheostomy report to recruit appropriate patients.

Patient population: Patients approached to consent for enrollment in the study will be participants admitted to Gaylord Hospital with tracheostomy who are medically stable for ambulation with Physical Therapy and for the use of PMV valve. All patients over the age of 18 will be considered for the study.

Enrollment criteria:

1. **Inclusion criteria:**
 - a) Individual with tracheostomy who can tolerate daily 30 minute PT session with use of PMV and be able to maintain oxygen saturations above 88% with exertion.
 - b) Ability to understand and respond to simple verbal instructions and one step commands in English well enough to consent without any Gaylord interpretation.
 - c) Ability to ambulate a minimum of 10 feet with/without assistive device and with/without physical assistance.
2. **Exclusion Criteria**
 - a) Active seizures
 - b) Active Pregnancy
 - c) Uncontrolled hypertension
 - d) Cognitive deficits that would disrupt ability to provide informed consent
 - e) Enteric infection control precautions
 - f) Ongoing orthostasis
 - g) Actively on decannulation protocol
 - h) Medical instability that would cause a doctor to put therapy program on hold

Intervention: Standard intervention vs use of PMV to assess ambulation distance during 6MWT. The 6MWT will be performed each session to assess ambulation distance, alternating standard vs PMV intervention on sequential days to compare results. BORG Rating of Perceived Exertion (RPE) scale will be utilized pre and posttest daily to assess patient's subjective rating of physical exertion levels. Oxygen saturations and heart rate will be monitored pre and posttest via oximeter as well as during test if medically necessary.

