Subject Assignment: Upon admission to Gaylord, appropriate patients are admitted under the inpatient program and tracked in the daily data pull of patient's with tracheostomy. Per hospital protocol, all patients will be evaluated by a physical therapist within the first 72 hours. If the patient meets criteria they will be asked to participate and then consented into the study by site investigators. Tracking forms will be compiled on inpatient therapy computers on research flash drive.

Study Timeline: Enrollment period will be 36 months and patients will receive two to six treatment sessions over a three week period. Treatment sessions will be scheduled in 30 minute increments to allot for testing time as well as collection of necessary data. Recruitment will remain open until we reach the goal of having 30 participants complete the full study. Partial data of early discharges, drop out due to changes in medical stability, or participants who are placed on

decannulation protocol during intervention period will still be included in the analysis. Data extraction will be retrieved from spreadsheets detailing results of 6MWT. Data will also be collected pre and post session on vital signs (HR and SaO₂) to monitor physiologic appropriateness of exercise response and patient's perceived rate of exertion via the BORG RPE scale.

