Primary outcomes: The primary outcome we wish to assess is participant **endurance** with or without a PMV attached to their tracheostomy tube. This will be assessed using two measures, the standardized 6MWT, and the Borg-RPE scale. While the reliability and validity of the 6MWT in patients with a tracheostomy tube haven't been extensively reported, it has been shown to have good validity and reliability in cardiopulmonary patients, patients with a diagnosis of chronic obstructive pulmonary disease (COPD)^{1,2}, and survivors of acute respiratory distress syndrome.³ Further, the American Thoracic Society have made recommendations for use of the 6MWT as a pre- post-treatment comparison for several conditions, including pulmonary rehabilitation.⁴ As such, we feel that it is valid to use 6MWT duration and distance as objective measures of participant endurance when comparing PMV and open tracheostomy. The Borg-RPE scale is a standardized subjective measure of an individual's perceived exertion upon completing an activity. The validity and reliability of Borg-RPE has been extensively assessed, and has been recommended as a valid measure to track patient progress during rehabilitation.⁵⁻⁹ For this study, pre- and post-6MWT Borg-RPE assessments will be collected. Paper copies and notes of both assessments will be collected during the study session and then later transcribed into an electronic data collection sheet made in Microsoft Excel.

Secondary outcomes: Participant endurance and response to completing the 6MWT with or without a PMV will also be assessed through other metrics, including pre- and post-6MWT heart rate; pre- and post-6MWT oxygen saturation; post-6MWT supplemental oxygen requirements; and 6MWT assistive device usage. In addition to being physiological indicators of participant exertion and endurance,^{10,11} several of these metrics have been found to positively correlate with the Borg-RPE scale.⁵⁻⁹ Notes of these metrics will be collected during the study session and then later transcribed into an electronic data collection sheet made in Microsoft Excel.

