General characteristics: Demographic characteristics that will be collected will include participant age, sex, and race/ethnicity. Other general characteristics that will be collected will include, as applicable, participant length of stay, discharge location, admitting diagnosis or condition that lead to tracheostomy, time to decannulation attempt, and decannulation attempt outcome. To promote study transparency and reproducibility, this information will be used to provide a descriptive overview of the study population to provide context for any reported findings. These data will be collected through manual review of Gaylord Hospital's electronic medical record system; they will be transcribed directly into an electronic data collection sheet made in Microsoft Excel.

Statistical Analysis

Data Analysis: Data were analyzed using GraphPad Prism (version 10; GraphPad Software, Boston, MA) and RStudio (version 4.2.2, Posit Software, PBC, Boston, MA].

Descriptive data is reported as mean (standard deviation). If hypothesis testing was done, data were reported with a p-value, and significance was set at $\alpha=.05$. Data were determined to be missing completely at random and were dealt with via complete case analysis. Data were also assessed for violations in assumptions of their given tests, and were dealt with via non-parametric analysis as necessary.

Paired t-tests or Wilcoxon tests were utilized as necessary to evaluate between-group differences in continuous outcome variables.

References:

1. Six Minute Walk Test / 6 Minute Walk Test [Internet]. Physiopedia. [cited 2022 Aug 5]. Available from: https://www.physio-pedia.com/Six_Minute_Walk_Test/_/6_Minute_Walk_Test
2. 6 Minute Walk Test [Internet]. Shirley Ryan AbilityLab. [cited 2022 Aug 15]. Available from: <https://www.sralab.org/rehabilitation-measures/6-minute-walk-test>
4. ATS Statement: Guidelines for the Six-Minute Walk Test. *Am J Respir Crit Care Med* [Internet]. American Thoracic Society - AJRCCM; 2002 Jul [cited 2022 Aug 15];166(1):111–117. Available from: <https://www.atsjournals.org/doi/10.1164/ajrccm.166.1.at1102>

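### Complete case analysis, on an unsupported missing-completely-at-random statement, may drop the early leavers whom the protocol promises to analyse; a mixed model on all sessions would keep them

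*Combined protocol and SAP*

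**What the plan says.** Three parts of the combined protocol and SAP bear on this point.

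- **Design.** Research design describes a "Six period Quasi-Randomized Crossover Controlled Study". Intervention has the two conditions "alternating standard vs PMV intervention on sequential days to compare results".
- **Partial data.** Study Timeline states that "patients will receive two to six treatment sessions" and that "Recruitment will remain open until we reach the goal of having 30 participants complete the full study". It then gives a rule for those who stop early: "Partial data of early discharges, drop out due to changes in medical stability, or participants who are placed on" the "decannulation protocol during intervention period will still be included in the analysis".
- **Missing data.** Data Analysis, written in the past tense, states: "Data were determined to be missing completely at random and were dealt with via complete case analysis". The tests it names for continuous outcomes are the paired t-test and the Wilcoxon test.

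Neither a complete case nor the full study is defined. The text also does not say how two to six sessions per person become one paired value.

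**The concern.** The protocol makes a commitment about early leavers, and the analysis section names a method that, on one reading, breaks it. The reader cannot tell who is in the comparison for either primary measure.

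The justification offered for the method is also weak where it matters most. Missing completely at random means that stopping is unrelated to anything about the participant. Two of the three named reasons for stopping are a change in medical stability and a move to the decannulation protocol, and both relate to health state. The text says that the mechanism was determined, but describes no comparison or reasoning.

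At stake are the information in the partial records and the population that the result describes: everyone with usable data, or only those who stayed for all six sessions.

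**Working it through.** **The texts side by side.** Three meanings of a complete case are open.

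- *One standard/PMV pair.* Conditions alternate and the tests are paired, so two consecutive sessions give a pair. Leavers with two or more sessions stay in, and the two sections agree.
- *All six sessions.* Participants with two to five sessions are dropped, against Study Timeline.
- *A non-missing reading.* The rule would cover only single lost values; under Primary outcomes, "Paper copies and notes of both assessments will be collected during the study session and then later transcribed". How leavers enter the paired tests is then not stated.

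**What dropping leavers could cost.** The documents give no session counts, SD or effect size, so there is no stated figure to reproduce. Everything below except the 30 is assumed.

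- Full participants: 30 (the recruitment goal), with three pairs each.
- Partial participants: m = 3, 10 or 20, with k = 1 or 2 pairs each.
- Unit: the SD of a single-pair difference.
- rho: within-person correlation of pair differences, from 0 to 1.
- D: difference in valve effect between partial and full participants.

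The variance of a participant's mean over k pairs is v(k) = rho + (1 − rho)/k. As a simplification, the mixed model is represented by precision weighting of participant mean differences, without the session effect. The weight on partial participants is

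w = (m/v(k)) / (30/v(3) + m/v(k)).

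At rho = 0 this reduces to m·k/(90 + m·k), which is weighting by number of pairs. For example, m = 10 and k = 1 give 10/100 = 0.10. Dropping partial participants shifts the estimate by w·D. Keeping them lowers the standard error by 1 − √(1 − w).

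| m | k | w at rho = 0 / 0.5 / 1 | SE reduction at rho = 0 / 1 |
|---|---|---|---|
| 3 | 1 | 0.03 / 0.06 / 0.09 | 1.6% / 4.7% |
| 10 | 1 | 0.10 / 0.18 / 0.25 | 5.1% / 13.4% |
| 20 | 1 | 0.18 / 0.31 / 0.40 | 9.5% / 22.5% |
| 3 | 2 | 0.06 / 0.08 / 0.09 | 3.2% / 4.7% |
| 10 | 2 | 0.18 / 0.23 / 0.25 | 9.5% / 13.4% |
| 20 | 2 | 0.31 / 0.37 / 0.40 | 16.8% / 22.5% |

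The w column is also the shift in SD units at D = 1, so 0.03 to 0.40. At D = 0.25 the range is 0.01 to 0.10. At D = 0 the shift is zero. For scale, the 95% confidence interval half-width with 30 full participants, t(0.975, 29)·√(v(3)/30), is 0.22, 0.30 and 0.37 at rho = 0, 0.5 and 1.

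**A case where keeping leavers does not help.** Suppose the paired test uses unweighted participant means. Its variance is (30·v(3) + m·v(k))/(30 + m)². At rho = 0 and k = 1 this is 13/1089, 20/1600 and 30/2500 for m = 3, 10 and 20, against 1/90 with full participants only. The standard error is then 3.7%, 6.1% and 3.9% larger with the leavers in. At rho = 0.5 or above, unweighted means also gain precision.

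**The case against.** The strongest reply is that this is a gap in reporting rather than an error. Study Timeline allows as few as two sessions and expressly keeps partial data, conditions alternate, and the tests are paired. Together these favour the one-pair reading, under which nobody with a pair is lost. That argument stands as far as it goes. A reader might infer that the two sections contradict each other, but the documents do not support this: they conflict only if a complete case means six sessions. The six-period label and the goal of 30 who complete the full study keep that meaning open without establishing it.

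A reader might also infer that the result is biased. Each participant is compared with themselves, so health state may change walking level without changing the valve contrast. Nothing in the documents shows a different valve effect in leavers. D, m, k and rho are all assumed, and m = 20 would mean 40% leaving early (20/50).

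Two further limits stand. No cause is given for early discharges, so not every named reason can be said to follow health state. And replacing the primary analysis after the results are known would be a post-hoc change; the fix below allows for that.

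What remains is that missing completely at random is asserted without support for a group in which it is doubtful, and that a better method is available for data already held.

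**Conclusion.** The point holds as a worthwhile improvement. The complete case method rests on an unsupported statement about why data are missing, and on one of the open readings it discards records that the protocol says will be used. On that reading precision is usually lost: about 1.6% to 22.5% in standard error under precision weighting, with the assumed numbers above. The loss is not universal, since unweighted means with one-pair leavers and rho = 0 go the other way. Bias requires D to differ from zero, and its size cannot be determined from the documents. On the one-pair reading nothing is lost by exclusion, and the gain is mainly clearer reporting and better use of unequal numbers of sessions.

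**What to change.** Analyse 6MWT distance, and likewise Borg RPE, with a linear mixed model on all available sessions: condition and session number as fixed effects, a participant random intercept and, if estimable, a participant-specific valve effect. This uses all partial data, as Study Timeline promises, and needs only missing at random.

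Because the analysis is already done:

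- report the paired test as it was run beside the mixed model, and label the model as added later;
- do not rely on missing completely at random for participants who left;
- state which meaning of a complete case was used, and report any exclusion of partial participants as a departure from Study Timeline.

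The cost is one re-analysis with no new data: results are held in spreadsheets and Data Analysis lists RStudio. The model still assumes missing at random, and with about 30 to 50 participants the variance of the valve effect may be poorly estimated. Simple weighting by number of pairs is best left out as a fallback. If it is used, say that it gives early leavers less weight than an average-patient effect would: with 20 one-pair leavers among 50 participants, 20/110 = 18% against 20/50 = 40%.

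### The paired tests ignore the day of each walk and no starting order is stated, so recovery over time can bias the valve comparison

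*Combined protocol and SAP*

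**What the plan says.** Research design calls the trial a "Six period Quasi-Randomized Crossover Controlled Study". Under Intervention, a walk is done each session, "alternating standard vs PMV intervention on sequential days to compare results". Study Timeline states that "patients will receive two to six treatment sessions over a three week period", and sets the target: "Recruitment will remain open until we reach the goal of having 30 participants complete the full study". Incomplete series also count; data from participants placed on a "decannulation protocol during intervention period will still be included in the analysis".

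The comparative analysis, under Statistical Analysis, is one sentence: "Paired t-tests or Wilcoxon tests were utilized as necessary to evaluate between-group differences in continuous outcome variables". It names no day, period or sequence term. It does not say how up to six walks become pairs. No section gives the quasi-randomization rule, the starting condition or a maximum interval within a pair; Subject Assignment covers only screening and consent.

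Primary outcomes supports both primary measures by their use in following change. For walking distance it cites "recommendations for use of the 6MWT as a pre- post-treatment comparison for several conditions, including pulmonary rehabilitation"; the Borg scale "has been recommended as a valid measure to track patient progress during rehabilitation".

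**The concern.** Pairing removes stable differences between people. It does not remove change within a person from one walk to the next. These are inpatients receiving physical therapy, followed for up to three weeks, and practice at the test may add to recovery. If the valve walk tends to follow the standard walk, part of the gain over time is credited to the valve; in the reverse order it is held against the valve. Strict alternation repeats the same order in each of a participant's pairs (walks 1-2, 3-4, 5-6), so more pairs do not dilute the error. Protection then depends on a balanced starting order, which the documents do not let a reader confirm.

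**Working it through.** The plan gives no power calculation, SD or trend, so there is no figure of its own to reproduce.

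**Inputs from the plan.** Alternating conditions; two to six sessions within three weeks; 30 completers; paired t or Wilcoxon test; alpha 0.05 (taken as two-sided).

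**Assumed inputs.** Within-person SD 30 m per walk; linear gain 3 m/day (range 1 to 5); share *p* starting on standard of 0.5, 0.7 or 1; gaps all 1 day, 20% at 4 days, or all 4 days. Distance only; nothing was computed for the Borg scale.

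**Step 1: how a trend enters.** Take evenly spaced walks, standard first, averaged by condition.
- Six walks: PMV at positions 2, 4, 6 (mean 4), standard at 1, 3, 5 (mean 3). The difference is one step of trend. Two and four walks give the same.
- Three walks: 2 against (1+3)/2 = 2, so a linear trend cancels. Five walks: 3 against 3, also cancels. The plan does not say walks are averaged this way.

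**Step 2: bias for an even number of walks.** Bias = rate × mean gap × (2*p* − 1). The mean gap with 20% at 4 days is 0.8×1 + 0.2×4 = 1.6 days. For example, 3 × 1.6 × 0.4 = 1.92 m at *p* = 0.7.

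**Step 3: type I error.** Simulated with six walks, 30 participants, no valve effect, 4000 runs.

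| Start on standard | Gaps | Bias (m) | Paired t |
|---|---|---|---|
| 50% | 1 day / 20% at 4 / all 4 | 0 / 0 / 0 | 0.051 / 0.046 / 0.032 |
| 70% | 1 day / 20% at 4 / all 4 | 1.2 / 1.9 / 4.8 | 0.057 / 0.065 / 0.136 |
| 100% | 1 day / 20% at 4 / all 4 | 3.0 / 4.8 / 12.0 | 0.101 / 0.175 / 0.739 |

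A model with participant, condition and day, with participant-clustered errors, gave 0.046 to 0.054 in all nine cases, with the mean estimate within 0.1 m of zero.

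**Step 4: trend of 1 to 5 m/day, 20% of gaps at 4 days.** At 70/30 the bias is 0.6 to 3.2 m (type I error 0.053 to 0.092). If all start on standard it is 1.6 to 8.0 m (0.065 to 0.40).

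**Step 5: equal mix of two to six walks, averaged by condition, valve effect varying between participants with SD 20 m.** Three of the five walk counts are even, so about 3/5 of the Step 2 bias remains. For example, 0.6 × 1.2 = 0.7 m. Simulated bias is 0.7, 1.0 and 2.9 m at 70/30 (type I error 0.05 to 0.07), and 1.9, 2.8 and 7.3 m if all start on standard (0.06, 0.07 and 0.17).

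**Step 6: balanced order, power for a 15 m effect, six walks.** Paired t against day model: 0.89 v 0.90 on consecutive days, about 0.89 v 0.90 with 20% of gaps at 4 days, and 0.85 v 0.90 with all at 4 days.

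**Step 7: a second set of assumptions.** Let *b* be the trend per session and *s* the SD of the per-participant difference net of trend. With *b* = 10 m, *s* = 40 m and 30 participants, all starting on standard gives +10 m and about 26% type I error (Wilcoxon about 25%). An 80/20 split gives 0.6 × 10 = 6 m and about 12%. With balanced order the standard error grows by √(1 + (30/29)(*b*/*s*)²) = √(1 + 1.034 × 0.0625) = 1.032, which takes 80% power to 77.5%. The growth is at most 12% while *b*/*s* is 0.5 or less, but 43% if *b* = *s* = 20 m.

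**The case against.** The strongest reply is that the design already contains the problem. Alternation limits the bias to one step of trend, and the wording points to walks on consecutive days. In the case nearest that text, with a 70/30 start, the result is 1.2 m and 0.057, which would change no conclusion. The 0.74 needs every participant to start on standard, six walks each, every gap at 4 days and an identical valve effect in everyone. Adding a valve-effect SD of 20 m cuts it to about 0.52. In the mix of two to six walks, inflation is slight even with a uniform start unless every gap is 4 days. The label quasi-randomized also makes a uniform start less likely. Finally, citing instruments as responsive to change does not show that these patients change between adjacent days.

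Much of this stands, and it fixes the size of the point: small in the mild case, material only when most participants start on one condition, more so with longer gaps. It does not remove the point. No rule or split is given, so the bad case cannot be excluded, and up to six sessions in three weeks leaves room for gaps.

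A second reply is that a linear day term is only a partial remedy. With a 10 m gain after the first walk and none later (six consecutive walks, all standard first), the paired bias is 10/3 = 3.3 m and the day model still leaves about 2.1 m. That is correct, but it is still less bias than the paired test carries.

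**Conclusion.** The concern holds. The stated tests have no protection against change over time, and the documents do not show that starting order was balanced. If order was unbalanced, the valve effect is biased by rate × mean gap × imbalance. If it was balanced, there is no mean bias and the loss of precision is small, provided the trend per session is no more than about half the SD of the paired difference. Every figure in metres rests on an assumed trend, SD, gap pattern and starting split, so the actual size is unknown. This is a change that should be made, held with medium confidence; it does not show that the trial's result is wrong.

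**What to change.** In Data Analysis, make the primary comparison a model on all walks with participant, condition and days since first walk (by calendar date). Use it by default, not only when distributional assumptions fail.

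Let the valve effect differ between participants, through participant-clustered errors, a random condition slope or a participant-level bootstrap. This matters: with balanced order on consecutive days, a condition-plus-day model without it rejects at 0.063, 0.107 and 0.166 for a valve-effect SD of 10, 20 and 30 m, against 0.048 to 0.051 with clustered errors.

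Report how many participants started on each condition and the mean PMV-minus-standard day difference. Keep the paired t or Wilcoxon test as a supporting analysis with a stated pairing rule, and add one restricted to consecutive-day pairs.

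The cost is analysis time only. The study is closed, so this is a reanalysis, and the plan already lists RStudio. It needs session dates, assumed recoverable from the paper session records or the medical record. Limits to state:
- It assumes roughly linear change within three weeks.
- Two-walk participants with the same order and gap do not help separate day from condition.
- If everyone started on the same condition, a linear day term can still be fitted from those with three or more walks, but a separate effect for each period could not be told apart from the valve.
- The random-slope version is slightly conservative (type I error 0.03 to 0.04) if the valve effect is the same in everyone.
- The consecutive-day analysis has fewer pairs.
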